5.2 PARTICIPANT EXCLUSION CRITERIA

- 1. Progressive neurological disease.
- 2. Clinical diagnosis of bipolar disease, panic disorder, psychosis or severe depression, or PHQ-9 score > 20
- 3. Patients with prior hospitalization related to depression or Electroconvulsive therapy.
- 4. History of suicidal ideation or intent in past or present
- 5. Clinical history or laboratory evidence of hepatic or renal insufficiency.
- 6. Pregnant or lactating women.
- 7. Current heavy alcohol use (>14 drinks per week for men or >7 drinks per week for women) or) known medical disorder related to alcohol use or current illicit drug use.
- 8. Patients with recent use (<1 month) or already taking fluoxetine or other selective serotonin reuptake inhibitors (SSRIs).
- 9. Concurrent use of monoamine oxidase inhibitors, antipsychotic agents, antidepressant agents other than SSRIs or frequent use of triptan agents (>2/week).
- 10. History of a previous allergic reaction or adverse effects with fluoxetine, hypersensitive reaction-anaphylaxis; laryngeal edema; hives
- 11. History of serotonin syndrome.
- 12. History of uncontrolled pulmonary or cardiac illness.
- 13. Patients with normal hypercapnic ventilatory response, i.e. HCVR slope of ≥ 2.0
- 14. Patients with known prolong QT interval
- 15. Patients with family history of prolong QT interval
- 16. Patients with family history of sudden cardiac death.

Version 01.2 Protocol:201607761 06/28/2017

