2.3.1 KNOWN POTENTIAL RISKS

Fluoxetine is a FDA approved antidepressant medicine which is used very frequently and safely. Some patients may experience some side effects that include: Nausea, diarrhea, anorexia, dry mouth, dyspepsia, insomnia, anxiety, nervousness, somnolence, tremor, decreased libido, abnormal dreams, headache, asthenia, flu like syndrome, fever, weight loss, Flatulence, constipation, rash, pruritus, abnormal vision etc. However, rare and serious side effects are also possible which include; worsening depression, increase suicidal thoughts or actions, mood swings, acting aggressive or violent, serotonin syndrome, severe allergic reaction- trouble breathing, swelling of face, tongue, eyes or mouth, rash, hives, abnormal bleeding if you are taking blood thinner coumadin warfarin (Coumadin®), a non-steroidal anti-inflammatory drugs (NSAIDs, like Ibuprofen or naproxen), or aspirin, increase in seizure frequency and possible irregular heart rhythm called Torsades de pointes due prolonged OT.

Fluoxetine is classified by FDA as category "C" for use in pregnancy which means there is a known risk of birth defect animal fetus but there are no adequate data and well-controlled studies in human. Stopping fluoxetine suddenly can cause serious symptoms including:

- Anxiety, irritability, high or low mood, feeling restless or changes in sleep habits
- Headache, sweating, nausea, dizziness
- Shaking, confusion etc

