7.6 PROHIBITED MEDICATIONS, TREATMENTS, AND PROCEDURES

Subjects will be asked to avoid starting any new medications that may be associated with interaction or lead to serotonin syndrome. These include antidepressants, antipsychotics, other SSRI agents, migraine medicine- particularly "Triptan family", linezolid, methylene blue. These medication can lead to "serotonin syndrome".

b: Subjects enrolled from neurology clinic

Version 01.2 Protocol:201607761 06/28/2017

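### Only SSRIs have a look-back at entry, and two drugs that section 7.6 links to serotonin syndrome are not named in the exclusion criteria

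*Combined protocol and SAP*

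**What the plan says.** Three rules in the combined protocol and SAP bear on drugs that interact with fluoxetine through serotonin.

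- Section 5.2, exclusion 8, deals with SSRIs: "Patients with recent use (<1 month) or already taking fluoxetine or other selective serotonin reuptake inhibitors (SSRIs". It covers current use and use within the past month.
- Section 5.2, exclusion 9, deals with the other classes: "Concurrent use of monoamine oxidase inhibitors, antipsychotic agents, antidepressant agents other than SSRIs or frequent use of triptan agents (>2/week". It states no period for drugs already stopped.
- Section 7.6 governs the treatment period: "Subjects will be asked to avoid starting any new medications that may be associated with interaction or lead to serotonin syndrome". Its examples are antidepressants, antipsychotics, other SSRIs, migraine drugs (the triptans in particular), linezolid and methylene blue, and it gives serotonin syndrome as the reason.

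Two further entries show that the protocol takes this risk seriously. Section 2.3.1 includes serotonin syndrome among the rare and serious effects of fluoxetine ("mood swings, acting aggressive or violent, serotonin syndrome"), and exclusion 11 bars anyone with "History of serotonin syndrome".

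**The concern.** The protocol identifies one hazard and names the drugs that bring it, but its rules do not follow those drugs consistently over time. An exposure can be recently ended, ongoing at entry or new on study. A reader would expect each named drug to be addressed in all three states, or a reason given where it is not.

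What is at stake is mainly participant safety. Staff who apply sections 5.2 and 7.6 exactly as written could randomise someone with an exposure that the protocol itself treats as hazardous, without breaching any rule. Two screeners could also decide the same case differently, because the text does not settle it.

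**Working it through.** No arithmetic underlies this point, and the plan gives no figure to reproduce. The check sets exclusions 8 and 9 (section 5.2) beside section 7.6, drug by drug.

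| Drug or class | Stopped shortly before entry | In use at entry | Started on study |
|---|---|---|---|
| SSRIs | Excluded if within 1 month (exclusion 8) | Excluded (8) | To be avoided (7.6) |
| Non-SSRI antidepressants | No rule | Excluded (9) | To be avoided (7.6) |
| Antipsychotics | No rule | Excluded (9) | To be avoided (7.6) |
| MAOIs | No rule | Excluded (9) | Not named as a class in 7.6; reached only through its general wording |
| Linezolid, methylene blue | No rule | Not named | To be avoided (7.6) |
| Triptans | No rule | Excluded only above 2 per week (9) | To be avoided, no threshold (7.6) |

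Three results follow.

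1. Only the SSRI row is filled in every column. The gap for recently stopped MAOIs, antipsychotics and non-SSRI antidepressants arises inside section 5.2, because exclusion 8 has a look-back and exclusion 9 has none.
2. For linezolid and methylene blue, section 7.6 reaches new starts only and section 5.2 names neither. Use ongoing at entry is therefore not expressly addressed in either section.
3. Triptans have a frequency threshold in one section and none in the other, with no stated reason.

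The next step was to look for a rule elsewhere that closes the gap.

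- Section 7.5.1 (precautionary medications) covers only NSAIDs, aspirin and blood thinners.
- Sections 7.1.1, 7.3.2, 7.3.3 and 7.3.4 and the schedule of events collect medication information at screening, enrolment and each later contact. None of them turns it into a further eligibility rule.
- Section 5.4.1 lets an investigator end participation when an exclusion criterion is met. It cannot act where no criterion covers the exposure.
- Exclusion 11 concerns a past episode of serotonin syndrome, not current or recent drugs.
- The Iowa SSRI screening questionnaire (section 7.3.1) may ask about these drugs, but its content is not in the documents.

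On size, the documents give no frequency for such use. For scale only, assume that 1% to 5% of the 40 randomised participants are affected: 0.01 × 40 = 0.4 and 0.05 × 40 = 2 participants. Both percentages are assumptions.

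**The case against.** The other side has several fair points.

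- **Linezolid.** A reader might infer that a patient already on linezolid is eligible. The documents do not establish this. Exclusion 9 uses class terms without a drug list and does not say whether linezolid falls under one of them, and the screening questionnaire is not shown. What the text supports is that linezolid and methylene blue are not named in 5.2. This part of the objection stands.
- **Triptans.** Accepting low existing use while discouraging new starts can be a coherent rule, so this is not a contradiction. It is a difference that the protocol leaves unexplained.
- **Other safeguards.** Exclusions 2 to 4 remove patients with bipolar disease, panic disorder, psychosis, severe depression, a PHQ-9 score above 20, a depression-related admission or suicidality. They plausibly shrink the group recently on these drugs. That lowers the likely number affected but leaves the look-back gap open.
- **HCVR endpoints.** A reader might also infer that wash-out of a recently stopped antidepressant would distort the HCVR results. Section 2.1 makes a serotonergic influence on CO₂ response plausible. However, the documents give no effect of non-SSRI wash-out on slope and do not say that exclusion 8 exists to protect the baseline. Even an assumed shift of 1 L/min/mmHg in one participant moves an arm mean by 1/20 = 0.05 with 20 per arm, or 1/10 = 0.10 with 10 per arm, and no SD is given against which to judge that. HCVR change is a secondary endpoint in a pilot that plans no inferential tests on it, and randomisation would spread such cases across both arms in expectation. Damage to the endpoint is not shown and is not claimed here.

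**Conclusion.** The point holds as a gap in the written rules. On the literal text, a patient who has just stopped an MAOI, an antipsychotic or a non-SSRI antidepressant meets no drug exclusion, and ongoing use of linezolid or methylene blue at entry is not expressly covered by either section. The different handling of triptans needs an explanation.

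It would be wrong to read the look-back gap as a conflict between the entry criteria and the prohibited-drug list. Section 7.6 says nothing about recently stopped drugs, so that gap belongs to section 5.2 alone. Nor does it extend to a patient just off an SSRI, whom exclusion 8 covers.

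The number affected cannot be derived from the documents and is probably small. The case for acting rests on the seriousness that the protocol itself gives to serotonin syndrome and on the low cost of the change. No sample size, power or error rate is involved. The conclusion assumes that no screening form outside these documents already applies a wider rule; even if one does, the written criteria should say so.

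**What to change.** Reconcile exclusions 8 and 9 with each other and with section 7.6, so that each drug or class the protocol names for this risk is addressed consistently for recent use, use ongoing at entry and new use on study. Where a difference is intended, as it may be for triptans, state it and give the reason. Check the reconciled rules against the medication history already taken at screening and at later contacts. Which drugs are listed, what intervals apply and how triptans are handled are for the sponsor's clinicians to decide; this review proposes none.

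The cost is amendment wording and IRB approval, with no new data collection. The downside is possibly a few more screen failures. Section 10.4.2 reports enrolment as a percentage of those screened, and section 5.3 expects about 100 HCVR screens. If those screens are the denominator, each participant lost in this way lowers that figure by about 1/100, or one percentage point.

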5.3 STRATEGIES FOR RECRUITMENT AND RETENTION

Patients, 18-75 year age, with epilepsy being treated at EMU & neurology clinic at the University of Iowa Hospital & Clinics will be screened for their eligibility for this study. Subjects with lack of consent capacity including severe mentally ill, prisoners, cognitive impaired, pregnant, children, prisoner, non English speaking and employee vounteers will be excluded from the study.

Approximately, 100 subjects will undergo HCVR testing for screening; Eligible subjects will be randomized to fluoxetine vs placebo, until each group has 20 completed subjects.

Anticipated accrual rate: 2/month

Number of sites and participants in US site: 1

Source of participants and Recruitment venues: Patients, 18-75 year age, with epilepsy being treated at EMU & neurology clinic at the University of Iowa Hospital & Clinics

Types of advertisements planned: Emails with information regarding the study will be distributed among neurology physicians working at the University of Iowa Hospitals & Clinics.

Subjects will be contacted via telephone as a part of study protocol followup which may improve retention.

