5.1 Study Leadership Error! Bo	
CONFLICT OF INTEREST POLICY Error! Bo	
LITERATURE REFERENCES Error! Bo	okmark not defined.
PENDIX Error! Bo	okmark not defined.

Version 01.2 Protocol:201607761 Version 01.2

LIST OF ABBREVIATIONS

SUDEP	Sudden unexpected and unexplained death in patients with epilepsy
HCVR	Hypercapnic Ventilatory Response
VE	Minute Ventilation
ETCO2	End tidal carbon dioxide
VRTCO2	Ventilatory recruitment threshold for carbon dioxide
EMU	Epilepsy Monitoring Unit

STATEMENT OF COMPLIANCE

The trial will be carried out in accordance with Good Clinical Practice (GCP) as required by the following (use applicable regulations depending on study location and sponsor requirements; examples follow): • United States (US) Code of Federal Regulations (CFR) applicable to clinical studies (45 CFR Part 46, 21 CFR Part 50, 21 CFR Part 56, 21 CFR Part 312, and/or 21 CFR Part 812) • ICH E6 All key personnel (all individuals responsible for the design and conduct of this trial) have completed Human Subjects Protection Training.

I agree to ensure that all staff members involved in the conduct of this study are informed about their obligations in meeting the above commitments.

Principal Investigator: _	[name]	
	Print/Type Name	
Q	mfgrð	
Signed:		Date: 6/28/2017

Version 01.2 Protocol:201607761 06/28/2017

PROTOCOL SUMMARY

Title: Abnormal ventilatory response to carbon dioxide in epilepsy patients: a

potential biomarker for seizure induced respiratory depression &

modification by SSRI- a pilot study

Précis: Double blind randomized phase II clinical trial.

Patients with epilepsy either undergoing video EEG study or being planned for one, will be screened by HCVR test. Fourty subjects with a depressed response (slope <2.0 L/mim/mm Hg) will be randomized to either

fluoxetine or placebo (1:1)

Intervention will be for 6 weeks.

Subjects will be enrolled in two different locations, EMU or neurology clinic. A follow up HCVR testing will be done at one month.

Continuous VEEG, and comprehensive respiratory monitoring (chest & abdominal belts, oro-nasal pressure & thermistry, pulse oximeter and trancutanesous CO₂ monitor) will be collected.

Change in the HCVR before and after intervention in two groups will be compared to determine effect of the drug. Similarly, differenc in severity of peri-ictal respiratory abnormalities will be compared between two arms.

Objectives: Primary Objective:

To assess feasibility of successfully enrolling subjects

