4 STUDY DESIGN AND ENDPOINTS

4.1 DESCRIPTION OF THE STUDY DESIGN

Double blind placebo-controlled randomized prospective trial

Two enrolling locations: EMU and Neurology Clinic

1) To test effect of Fluoxetine on HCVR: Subjects will be screened in the EMU and neurology clinic. Subjects eligible are those with patients with epilepsy who have a reduced baseline HCVR slope (<2.0 L/min/mmHg). Subjects will be enrolled, and randomized to either fluoxetine or placebo (1:1) until 20 subjects complete the study. Investigational Drug Services (IDS), at the University of Iowa Hospitals and Clinics (UIHC), will be responsible for randomizing and dispensing the

Version 01.2 Protocol:201607761 Version 20.2 Version 01.2

drugs. Both fluoxetine and placebo will be encapsulated in identical casing to mask their identity. Both the subjects and the investigators will be blinded to the randomization process. A standard titration plan will consist of fluoxetine or placebo 10 mg per day for a week, then 20 mg per day for a week and then 40 mg per day for 2 weeks, upon discharge. Subjects will return after 4 weeks for follow up HCVR testing in the Clinical Research Unit at UIHC. For each subject, the magnitude of post-treatment HCVR in terms of HCVR slope, minute ventilation, VRTCO₂, time to VRTCO₂ and time to target ETCO₂ at the end of the study will be compared with their baseline HCVR. The medication adherence rate, safey concerns and change in mood scale will be assessed at follow up. Reported adverse effects will be collected for all subjects. Enrolment rate and study completion rates will also be assessed every 6 months.

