5.5 PREMATURE TERMINATION OR SUSPENSION OF STUDY

Circumstances that may warrant termination or suspension include, but are not limited to:

- Determination of unexpected, significant, or unacceptable risk to participants
- Poor recruitment and/or completion rates

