10.6 MEASURES TO MINIMIZE BIAS

10.6.1 ENROLLMENT/ RANDOMIZATION/ MASKING PROCEDURES

Subjects will be screened and enrolled in two locations, neurology clinic and EMU. A total of 20 subject will be enrolled in each location and they will be randomized to drug vs placebo group equally (1:1) using computer generated random numbers. The assignment for each subject will be kept in a sealed envelope and will be provided to investigational drug pharmacy at the University of Iowa.

The participants as well as the investigators (except one) will be blinded to the drug the participant is receiving. Bottles of the study drug will be labelled with the name of study, drug A or drug B, and instruction of titration plan.

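### Enrolment closes at 40 randomised in the Précis and 10.6.1 but at 40 completed in 4.1 and 5.3; the protocol needs one target

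*Combined protocol and SAP*

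**What the plan says.** Two places count subjects at entry:

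- Protocol Summary, Précis: "Fourty subjects with a depressed response (slope <2.0 L/mim/mm Hg) will be randomized to either" fluoxetine or placebo.
- Section 10.6.1: "A total of 20 subject will be enrolled in each location", then randomised 1:1. With two locations that is 40.

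Two sections count subjects at the end:

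- Section 4.1, part 1 (effect on HCVR): "randomized to either fluoxetine or placebo (1:1) until 20 subjects complete the study". Part 2 (peri-ictal respiration) has the same rule, again with 20 completers.
- Section 5.3: randomisation continues "until each group has 20 completed subjects".

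On timing, section 5.3 gives "Anticipated accrual rate: 2/month" and about 100 subjects tested for screening. The Protocol Summary gives 2 years for the study and 6 weeks per participant, and section 7.3.4 places the last contact at week 7. Section 10.5 says there is no formal sample size calculation. No dropout allowance appears anywhere.

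**The concern.** A rule that stops at the 40th randomisation and a rule that stops at the 40th completion are the same only if nobody drops out. Otherwise the second replaces every dropout and randomises more people over a longer period. Section 10.6.1 describes equal allocation for 20 per location and makes no provision for replacements.

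Section 5.3 has a further ambiguity. Its word for the unit that must reach 20 completers could mean treatment arm or location. If it means arm, someone must count completers by arm in a blinded trial in order to know when to stop. If it means location, nobody need do so.

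This is a feasibility trial whose primary endpoints are recruitment and retention, so the number it sets out to recruit, and whether that number fits the stated time, is a central planning figure. Staff following different sections would close enrolment at different times.

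**Working it through.** There is no sample size formula to reproduce, so the check is of totals and calendar time.

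**Inputs.** Target 40 (Précis, 4.1, 5.3, 10.6.1); accrual 2 per month (5.3); study 24 months and participation 6 weeks (Protocol Summary); follow-up visit at week 4 (7.3.3); last call at week 7 (7.3.4). In months, 6 weeks = 1.38 and 7 weeks = 1.61. Assumption: 2 per month counts randomised subjects over both locations together.

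**1. Totals.** Section 10.6.1: 20 + 20 = 40 enrolled. Section 4.1: 20 + 20 = 40 completers, taking the two parts as separate subjects. Section 5.3: 2 × 20 = 40 completers, whether the unit is arm or location.

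**2. Forty randomised.** 40 / 2 = 20 months of accrual. Adding follow-up gives 20 + 1.38 = 21.4 or 20 + 1.61 = 21.6 months. Both lie inside 24.

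**3. Forty completed.** Number that can be randomised: N = 2 × (24 − follow-up). Largest dropout that still leaves 40 expected completers: 1 − 40/N.

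| Reading | Accrual months | N | Limit on N as it stands | Limit on whole subjects |
|---|---|---|---|---|
| Follow-up outside the 2 years | 24.00 | 48.0 | 16.7% | 16.7% (48) |
| Week-4 visit inside | 23.08 | 46.2 | 13.3% | 13.0% (46) |
| 6 weeks inside | 22.62 | 45.2 | 11.6% | 11.1% (45) |
| Week-7 call inside | 22.39 | 44.8 | 10.7% | 9.1% (44) |
| 6 weeks inside, plus 2 months start-up or close-out | 20.62 | 41.2 | 3.0% | 2.4% (41) |
| 2 per month at each location, 6 weeks inside | 22.62 | 4 × 22.62 = 90.5 | 55.8% | 55.6% (90) |

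If 2 per month counted subjects tested for screening, only about 45 would be tested in the time, against about 100 planned. At the plan's implied yield of 40 in 100 that gives about 18 randomised, and neither target is reached.

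**4. Illustrative dropout rates (assumed; none is in the documents).** Randomised = 40/(1 − d), rounded up. Total months = randomised/2 + 1.61.

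| Dropout | To randomise for 40 completers | Total months | Completers if 40 randomised |
|---|---|---|---|
| 10% | 44.4 → 45 | 24.1 | 36 |
| 15% | 47.1 → 48 | 25.6 | 34 |
| 20% | 50 | 26.6 | 32 |

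At 15%, 47 is just short, since 47 × 0.85 = 39.95.

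**5. The limits are expected values.** With 45 randomised, the binomial chance of at least 40 completers is about 62% at 11.1% dropout, 71% at 10%, 31% at 15% and 9% at 20%.

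**The case against.** The stakes are modest. There is no hypothesis (10.2), no sample size calculation (10.5) and no inferential testing of efficacy (10.4.1). A target in completers also has a sound rationale. The analysis set is per protocol (10.3), the pilot exists to produce estimates (10.1), and subjects who withdraw after randomisation give no further outcome data (5.4.2). All of this stands. It is why neither target should be called the right one, but it does not make the two rules compatible.

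Three stronger readings are tempting, and the documents do not support them.

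- A reader might infer that the same data would yield different recruitment and retention rates under the two targets. Section 10.4.2 defines both endpoints as counts per 3 months and as percentages of patients screened, and neither uses the target. The same data give the same rates; only the stopping point moves.
- A reader might infer that the conflict removes the reference for "Poor recruitment and/or completion rates" in section 5.5. That criterion has no numeric threshold under either target, and settling the target would not supply one.
- A reader might infer that the completer rule cannot be met in 2 years. With no stated dropout rate and an undefined accrual rate, that does not follow. Even at an assumed 15 to 20% dropout the overrun is about 1.6 to 2.6 months on an anticipated rate.

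**Conclusion.** The contradiction is explicit, needs no assumption, and is not resolved anywhere in the documents. It should be corrected.

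The timeline point is secondary and conditional. If 2 per month counts randomised subjects over both locations, 40 randomised fits the 2 years with more than two months to spare, while 40 completers leaves room for only about 9 to 11% dropout with follow-up inside the 2 years. If the rate applies to each location separately, there is no misfit. What can be said with confidence is that the plan does not give the figures needed to tell: what the accrual rate counts, and what dropout is expected.

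One consequence for retention does follow. Under the completer rule the final number completed is 40 by design, so dropout shows only in how many were randomised, and 10.4.2 does not use that number as a denominator.

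**What to change.** State one target, in the same words, in the Précis, 4.1, 5.3 and 10.6.1. Either choice is coherent:

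- **40 randomised:** 20 per location, enrolment closes at the 40th randomisation, withdrawals are not replaced, and 4.1 and 5.3 are reworded so that 40 means randomised. Cost: 4 to 8 fewer completers at an assumed 10 to 20% dropout.
- **40 completed:** state the dropout assumption, a cap on the number randomised and the resulting duration, say how replacements are allocated in 10.6.1, and say in 5.3 whether the 20 applies to arm or location. Cost: for example, 8 to 10 more subjects randomised and about 25.6 to 26.6 months at an assumed 15 to 20% dropout.

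Under either choice, say in 5.3 whether 2 per month counts subjects tested, enrolled or randomised, and whether it is per location or overall.

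In 10.4.2, add retention as completers over subjects actually randomised, beside the percentage of screened. For the 3-monthly reports, use those randomised and due to have completed. A fixed denominator of 40 should not be used: at 2 per month only about 6 would be randomised by month 3, and after a recruitment shortfall it would count people never randomised as not retained.

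Apart from the costs given above, this is a change of wording in those five places.
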